4.4 Variables

The following variables will be assessed at baseline independent of their acceptance to participate in the INKA Trial

1. Age
2. Sex
3. Disease duration

4. Height (meters)
5. Body weight (kg)
6. Type of scheduled arthroplasty (Total vs Unicdylar prosthesis)
7. The Oxford Knee Score (OKS)
8. Health outcome and quality of life survey (EuroQoL questionnaire)
9. Use of analgesics
10. The Knee injury and Osteoarthritis Outcome Score (KOOS) – 12 item short form
11. Patient’s global assessment of impact of the knee in daily life (PGA)
12. Illness perception questionnaire

Table 1: Collected baseline characteristics

Characteristics	Patients accepting INKA group	Patients declining nINKA group	Standardised Difference
Total, no. (%)			
Age, year			
Gender:			
Females, no. (%)			
Males, no. (%)			
Disease duration, years			
Height, meters			
Weight, kg			
Type of scheduled arthroplasty:			
Total knee arthroplasty, no. (%)			
Unicdylar knee arthroplasty, no. (%)			
The Oxford Knee Score (OKS)			
EuroQoL Index			
EuroQoL VAS			
Regular use of analgesics no. (%)			
Paracetamol/acetaminophen			
NSAIDs			
Acetylic acids			
Opiods			
The Knee injury and Osteoarthritis Outcome Score (KOOS) – 12 item short form:			

Pain score			
Function score			
QoL score			
Patient's global assessment of impact of the knee in daily life (PGA)			
Illness perception questionnaire:			
Item 1, score			
Item 2, score			
Item 3, score			
Item 4, score			
Item 5, score			
Item 6, score			
Item 7, score			
Item 8, score			

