Conflict of interest declaration

None declared.

SUMMARY

Background: Overweight is a main and modifiable risk factor for developing knee osteoarthritis (OA). Studies indicate a beneficial effect of weight loss on the symptoms of knee OA. The Intensive diet vs Knee Arthroplasty (INKA) trial is a RCT, which aims to assess weight loss as a non-inferior intervention and/or an alternative to surgical knee arthroplasty in overweight and obese patients suffering from knee OA. As RCTs carry a risk for selection bias and thereby risk for low external validity, comparison of the recruited trial participants and the invited participants, who decline trial participation will enable assessment of the external clinical validity and generalizability of the INKA trial

Objective: The objective of this study is to compare baseline characteristics of overweight knee OA patients accepting vs. declining enrolment in the INKA trial to explore if enrolled patients differ systematically from the declining participants with respect to both measured as well as unmeasured baseline characteristics.

Design: Cross-sectional study collecting baseline characteristics of patients with Knee OA eligible for enrolment in the INKA trial, whether accepting or declining enrolment.

Setting: Potential trial participants will be identified during their routine visits in the orthopaedic outpatient clinics at Copenhagen University Hospital Bispebjerg-Frederiksberg and Copenhagen University Hospital Amager-Hvidovre.

Participants: Adults ≥ 18 years old, obese ($BMI \geq 30 \text{ kg/m}^2$), with an indication for primary knee arthroplasty (unicondylar or total arthroplasty) due to knee OA are included either with consent or refusal to participation in the INKA trial. We will recruit 400 patients in total, 200 in each group.

Measurements: Baseline characteristics for the 2 groups are obtained extracting data from the participants' medical records including questionnaires answered by all patients, of which the main is The Oxford Knee Score (the primary outcome for INKA participants).

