4.3 Participants

All patients found eligible in INKA study (inclusion criteria for INKA) and accepting and declining enrolment in the INKA study are invited to participate in our study. We report the number of patients assessed for eligibility and reasons of exclusion. Study participants will be adults (i.e. at

least 18 years old), have a diagnosis of knee osteoarthritis with an indication for primary knee arthroplasty (unicondylar or total arthroplasty), and be obese ($BMI \geq 30 \text{ kg/m}^2$). An individual will be eligible for study participation if he/she meets the following criteria:

1. Age 18 or more
2. A clinical and radiological diagnosis of knee OA
3. $BMI \geq 30 \text{ kg/m}^2$
4. Motivated for weight loss as by the provided program
5. Signed informed consent.

A possible participant will, however, be excluded from the study if he/she meets any of the following criteria:

1. The scheduled surgery is for revision of an existing prosthesis
2. Planned surgery for more than one knee within the observation period
3. KA indication due to sequelae of fracture(s)
4. Injection of medication or substances in the target knee within 3 months prior to participation
5. Immuno-inflammatory arthritis as cause of the knee OA
6. Current systemic treatment with glucocorticoids equivalent to $> 7.5 \text{ mg}$ of prednisolone/day
7. Previous or planned obesity surgery
8. Inability to understand or read Danish incl. instructions and questionnaires
9. Any other condition or impairment that, in the opinion of the investigator (or his/her delegate), makes a potential participant unsuitable for participation or which obstruct participation.

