4.6.2 Body weight

The participants body weight is transferred from the medical records of their visit in the orthopaedic outpatient clinic.

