4.8 Bias and confounding variables

Confounding is an important concept in epidemiology, because, if presents, it can cause an over- or underestimate of the observed association between exposure and health outcome. The distortion introduced by a confounding factor can be large, and it can even change the apparent direction of an effect. However, unlike selection and information bias, it can be adjusted for in the analysis.

The challenge with observational data (like the proposed comparison) is that the groups (INKA vs nINKA) are not applied randomly, leading to selection bias and thus potentially confounding variables. For example, when we study the impact entering a “promising weight loss trial” before having direct access to a KA, and we compare the outcome among those (who accept the invitation to join the INKA trial) versus all of those who declined, we would potentially have some selection bias, as those who decline are different per definition. The difference can range from baseline characteristics that would influence the outcome; i.e., an advanced disease stage that make any potential delay of the surgery intolerable, or failure/ineffectiveness of previous weight loss trials. Or it can be a characteristic with neglectable effect on the outcome, ie., not having the time or the desire to be included in a clinical trial. Improved confounding variable balance (i.e. de-confounding) between INKA and nINKA groups can be achieved by matching observations from each group based on the propensity score, which in this case would be the probability that a patient accept participation in INKA given the observed covariates.

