4.9 Statistical methods

We will use the term balance diagnostics to describe the methods we use to assess whether the distribution of baseline covariates is similar between the two groups (INKA and nINKA, respectively). We designed the study to compare the mean (or medians) of continuous variables or the prevalence of dichotomous baseline covariates between INKA and nINKA participants. We will report the means and/or medians of continuous variables and the distribution of categorical variables for each of the two groups. These crude comparisons (between INKA=treatment and nINKA=control, respectively) will enable an assessment of the comparability of the two groups which will be indicative of the generalizability of the INKA trial (24).

Standardized differences for comparing means and prevalences between groups: For continuous variables, the standardized difference is defined as

$$d = \frac{(\bar{x}_{\text{treatment}} - \bar{x}_{\text{control}})}{\sqrt{\frac{s_{\text{treatment}}^2 + s_{\text{control}}^2}{2}}}$$

where x 's denote the sample means of the covariate in treated (INKA) and control (nINKA) participants, respectively, while the s^2 's denote the sample variance of the covariate in the groups. For dichotomous variables, the standardized difference will be defined as

$$d = \frac{(\hat{p}_{\text{treatment}} - \hat{p}_{\text{control}})}{\sqrt{\frac{\hat{p}_{\text{treatment}}(1 - \hat{p}_{\text{treatment}}) + \hat{p}_{\text{control}}(1 - \hat{p}_{\text{control}})}{2}}}$$

where p 's denote the prevalence or mean of the dichotomous variable in treated (INKA) and control (nINKA) participants, respectively.

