By using the standardised differences, it allows for the comparison of the relative balance of variables measured in different units (e.g. age in years with a 'Timed Up and Go'). Unlike t-tests and other statistical tests of hypothesis, the standardized difference is not influenced by sample size. Thus, the use of the standard difference will be used to compare balance in measured variables between treated and untreated subjects. Standardized differences are increasingly being used to compare balance in baseline covariates between groups in the propensity-score matched samples. A limitation to their use is lack of consensus as to what value of a standardized difference denotes important residual imbalance between treated and untreated subjects in the matched sample. While there is no clear consensus on this issue (24), as illustrated in the figure above, we will apply a standardized difference of ≥ 0.2 to indicate that there might be a meaningful imbalance in the baseline covariate (i.e. possibly poor generalizability); whereas a standardized difference ≥ 0.8 will be considered as definitive incomparability.

We will also apply the PROC NPAR1WAY procedure (using SAS software) to compute empirical distribution function (EDF) statistics, to statistically test the distribution of the baseline variables. PROC NPAR1WAY provides a summary of the Wilcoxon scores for the analysis baseline variable by class level (INKA and nINKA, respectively). It also displays the one-way ANOVA statistic, which for Wilcoxon scores corresponds to the Kruskal-Wallis test: If the statistical test indicates that there might be difference between groups <0.05 this ($P<0.05$) leads to rejection of the null hypothesis that the groups are similar.

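### BMI defines entry to the trial but is not a row in the balance table, so degree of obesity gets no direct balance result (minor; free to fix)

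*Combined protocol and SAP*

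**What the plan says.** The Summary (Participants) describes the population as "Adults ≥ 18 years old, obese", with BMI of at least 30 kg/m2. Section 4.3 repeats this: patients must have "an indication for primary knee arthroplasty (unicondylar or total arthroplasty), and be obese", with the same cut-off, and BMI appears again as a numbered inclusion criterion.

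Section 4.4 lists twelve baseline variables. Those on body size are "Height (meters" and "Body weight (kg". Table 1 carries the same two rows and no BMI row. Section 4.6.2 says only that "The participants body weight is transferred from the medical records of their visit in the orthopaedic outpatient clinic".

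Section 4.9 applies its methods to the baseline variables. It promises "We will report the means and/or medians of continuous variables", a standardised difference for each variable, and an NPAR1WAY test at P<0.05. A standardised difference of 0.2 or more is used "to indicate that there might be a meaningful imbalance in the baseline covariate (i.e. possibly poor generalizability"; 0.8 or more counts as definitive incomparability. The propensity model takes all collected baseline variables.

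**The concern.** The study asks whether patients who accept a weight-loss trial resemble those who decline it. How obese the two groups are is an obvious comparison, and BMI is the measure by which the protocol defines its population. The balance rules work row by row, and BMI has no row.

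Weight mixes BMI with height. Height varies within and between the sexes, which adds spread to weight that has nothing to do with obesity. A BMI difference above the plan's lower threshold may then sit below it in the weight row. A reader of the published table could not repair this: means of height and weight allow the BMI contrast to be approximated, but the two separate SDs do not give the SD of BMI.

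**Working it through.** **The omission.** BMI appears in the Summary and section 4.3 as an eligibility criterion. It does not appear in section 4.4, Table 1, section 4.6.2 or section 4.9. The variable list and table are intact, so this is not redaction or a lost figure. The plan gives no obesity balance figure that could be reproduced.

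**Inputs.** From the documents: thresholds 0.2 and 0.8, P<0.05, 200 patients per group. Assumed, because the documents give no mean or SD for height, weight or BMI: 55% women among decliners; mean height 1.65 m (women) and 1.78 m (men), SD 0.065 m within sex; mean BMI 36 in acceptors and 35 in decliners; BMI SD 3.5 to 5.5.

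**Step 1: attenuation, equal sex mix, BMI independent of height.** Write weight = B × H, with B = BMI and H = height squared. Then

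weight d / BMI d = 1 / √[1 + CV²(H) × (1 + mean² / SD² of BMI)].

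- Mean of H = 0.55 × 1.65² + 0.45 × 1.78² + 0.065² = 2.927. Its variance under the same assumptions is 0.0986, so CV²(H) = 0.0986 / 2.927² = 0.0115.
- Average squared mean BMI = (35² + 36²) / 2 = 1260.5.
- SD 4: 1 / √[1 + 0.0115 × (1 + 1260.5/16)] = 0.72.
- SD 5: 1 / √[1 + 0.0115 × (1 + 1260.5/25)] = 0.79.
- SD 5.5: 1 / √[1 + 0.0115 × (1 + 1260.5/30.25)] = 0.82.

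Simulation gives the same ratios, and 0.67 at SD 3.5. The weight row reaches 0.2 only when BMI d is 0.2/0.72 = 0.28, 0.2/0.79 = 0.25 or 0.2/0.82 = 0.24 (SD 4, 5, 5.5).

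**Step 2: vary the independence assumption.** In simulation the ratio rises to about 0.8 to 0.9 at a within-sex BMI-height correlation of -0.2 to -0.3. The BMI difference at which the weight row flags then falls to between 0.2/0.8 = 0.25 and 0.2/0.9 = 0.22. With slightly different inputs (60% women, BMI SD 4.5), a correlation of -0.6 gives 0.261/0.267 = 0.98, so attenuation almost disappears; a correlation of +0.2 gives 0.196/0.267 = 0.73.

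**Step 3: sex mix, BMI SD 4, BMI d = (36 - 35)/4 = 0.25.** Mean weight in decliners is 35 × 2.927 = 102.5 kg; the SD of weight is about 16.2 kg.

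| Women, acceptors vs decliners | Mean weight, acceptors | Weight d |
|---|---|---|
| 55% vs 55% | 36 × 2.927 = 105.4 kg | 2.93/16.2 = 0.18 |
| 62% vs 55% | 36 × 2.896 = 104.3 kg | 1.80/16.1 = 0.11 |
| 48% vs 55% | 36 × 2.959 = 106.5 kg | 4.05/16.3 = 0.25 |

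In the second line, sex d is 0.07/√[(0.62 × 0.38 + 0.55 × 0.45)/2] = 0.14 and height d is about -0.10. No existing row reaches 0.2, although BMI does. In the third line the weight row reveals the difference.

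**Step 4: finite samples.** 20,000 simulated studies of 200 vs 200; equal sex mix, BMI independent of height, BMI SD 4, 5, 5.5. At a true BMI d of 0.25, a BMI row would be flagged on d in about 69% of studies. BMI would be the only flag among sex, height, weight and BMI in 27%, 20%, 18% on d alone, and in 35%, 28%, 25% with d and the P<0.05 test applied to every row. With both screens, the lone-flag figure falls to 10%, 4%, 2% at a true d of 0.4 and to 2% or less at 0.5. With no true difference, the extra row adds a lone false flag in about 4% of studies.

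**The case against.** The strongest reply is that nothing is lost. Height and weight are collected, BMI must be known for eligibility, and any analyst can compute it. That limits the severity, but the plan as written still produces no BMI result, and a row added after the data are seen would be post hoc. The screening log is an appendix not shown, so one can say only that the available text does not derive BMI.

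The propensity model is a second reply. It enters sex, height and weight together, so its weight term given the other two largely carries the BMI contrast. This narrows the gap without closing it, because the plan promises no balance figure for BMI from that model.

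Third, the size is not established by the documents. It depends on assumed distributions and shrinks with a negative BMI-height correlation. The simulated true difference of 0.25 lies inside the band where the two rows can disagree, and nothing in the documents makes that value likely. At BMI SD 5.5, a contrast of 36 vs 35 gives d = 1/5.5 = 0.18, which a BMI row would not flag either. All this stands.

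A reader might also infer that section 4.8 recognises the need for BMI where it mentions "failure/ineffectiveness of previous weight loss trials" as a possible difference between the groups. It does not: that is treatment history, given as an illustration, and a BMI row would not measure it.

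**Conclusion.** The omission is a fact of the text: the characteristic that defines the population is not among the rows to which the 0.2/0.8 rule and the NPAR1WAY test apply. This does not depend on any assumption.

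Its consequence is minor. Under the assumptions above, the weight row understates the BMI difference by roughly 20% to 30% with independence, 10% to 20% at a correlation of -0.2 to -0.3, and hardly at all at -0.6. Sex imbalance moves it either way. What can be missed is a BMI imbalance just above 0.2, a level the plan itself treats only as a possible problem.

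A reader might infer that the study cannot detect differences in obesity, or that the weight row always understates them. The documents support neither. Larger imbalances would normally appear in the weight row, and fewer women among acceptors can raise the weight difference to the size of the BMI difference. No sample size or primary result changes.

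**What to change.** - Add to section 4.4: *Body mass index (kg/m2), derived as recorded weight / height squared.*
- Add a Table 1 row, *BMI, kg/m2*, under the same 0.2/0.8 rule and NPAR1WAY test as the other rows.
- Keep the height and weight rows, and base statements on obesity imbalance on the BMI row.

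Whether the propensity model uses BMI or height and weight can be left to the trial statistician; if all three are entered, near-collinearity should be expected.

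The cost is one derived variable and one table row, with no new data collection, plus the small extra chance of a lone false flag given above.

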4.5 Data sources/measurements

4.5.1 The Oxford Knee Score (Primary Outcome)

The Oxford Knee Score (OKS) is a 12-item Patient Reported Outcome questionnaire developed specifically to assess the patient's perspective on the outcomes of knee arthroplasty (KA) with respect to combined pain and physical function. Standardized answer options are given (5 Likert boxes) and each question is assigned a score from 0 to 4. Thus, a total score is calculated that ranges from 0 and 48, with 48 indicating the best outcome. The OKS is short, practical, reliable, valid, and sensitive to clinically important changes over time (16).

4.5.2 Health outcome and quality of life survey (EQ-5D-5L)

EQ-5D-5L is a standardized patient-reported instrument for use as a measure of health outcome and quality of life. EQ-5D-5L is designed for self-completion by respondents and is ideally suited for use in surveys.

The EQ-5D-5L consists of a descriptive system and the EQ Visual Analogue scale (EQ VAS). The descriptive system comprises 5 dimensions (mobility, self-care, usual activities, pain/discomfort, and anxiety/depression). Standardized answer options are given (5 Likert boxes) and each question

is assigned a score from 1 to 3. It is simple, taking only a few minutes to complete. Instructions to respondents are included in the questionnaire.

The EQ-5D VAS records the respondent's self-rated health on a 20 cm vertical, visual analogue scale with endpoints labelled '*the best health you can imagine*' and '*the worst health you can imagine*'. This information can be used as a quantitative measure of health as judged by the individual respondents.

4.5.3 Analgesic use

At clinical outcome assessment visit, the participants will be interviewed by an investigator about their use of analgesics since last visit. The interview will be focused on intake of

1. Paracetamol/acetaminophen
2. NSAIDS
3. Acetylic acids
4. Opioids

The use of these analgesics will be recorded as a 0-3 points Likert scale (0, never; 1, rarely; 2, 2-3 times per week; 3, daily or almost daily).

4.6 The Knee Injury and Osteoarthritis Outcome Score – 12 item short form (KOOS-12)

KOOS-12 is a 12-item measure derived from the original 42-item Knee injury and Osteoarthritis Outcome Score (KOOS) (17,18). KOOS-12 contains 4 KOOS Pain items, 4 KOOS Function (Activities of Daily Living and Sport/Recreation) items, and 4 KOOS Quality of Life (QOL) items (19). KOOS-12 provides scale scores for knee-specific Pain, Function and QOL, along with a summary measure of overall knee impact. KOOS-12 is intended to elicit people's opinions about the difficulties they experience due to problems with their knee and covers aspects of pain, functional limitations and knee-related quality of life.

Reliability, validity and responsiveness of the KOOS-12 scales have been shown to be acceptable (19) and there is evidence that supports the use of KOOS-12 for evaluating joint replacement outcomes (20).

Each item is scored from 0 to 4, left to right, with 0 representing no knee problems and 4 representing extreme knee problems. The separate KOOS-12 Pain, Function and QOL scale scores are calculated using the method of summated ratings, in which item responses in a scale are simply summed. KOOS-12 scale scores are transformed so 0 is the worst possible and 100 is the best possible score.

The KOOS-12 Summary knee impact score is calculated as the average of the KOOS-12 Pain, KOOS-12 Function and KOOS-12 QOL scale scores. A Summary impact score is not calculated if any of the three scale scores are missing. The KOOS-12 Summary impact score also ranges from 0 to 100, where 0 is the worst possible and 100 is the best possible score.

4.6.1 Patient's global assessment of impact of the knee in daily life (PGA)

The participant's assessment of the impact of their knee on everyday life is measured as the response to the question "*Taking into account all the activities you have during your daily life, your level of pain, and your functional impairment, how much does your [left/right] knee impact your daily life?*". A 100 mm visual analogue scale (VAS) will be used as assessment instrument with anchors: 0 = "*No impact*" and 100 = "*Worst imaginable impact*". The actual question asked will be in Danish.

4.6.2 Body weight

The participants body weight is transferred from the medical records of their visit in the orthopaedic outpatient clinic.

4.6.3 Brief Illness perception questionnaire (B-IPQ)

B-IPQ is a generic 9-item questionnaire developed to rapidly assess the cognitive and emotional representations in a variety of illnesses. B-IPQ is a short version of the 84-item revised illness perception questionnaire (IPQ-R) (21). B-IPQ assesses perceptions on the following five

dimensions: Identity, Cause, Timeline, Consequences and Cure-Control. Five of the items assess cognitive illness representations; two of the items assess emotional representations; and one item assesses illness comprehensibility. The ninth item is a free text field in which the respondent can formulate their beliefs about their condition (cause). We will not use this field in our study.

The first 8 items are scored on a 0-3 Likert scale with descriptors (none or extreme) at either end. The B-IPO scores have shown good test-retest reliability and adequate concurrent, discriminative, and predictive validity amongst patient samples with musculoskeletal disorders and other chronic disorders (22,23).

